Dental caries and its tremendous effects are considered one of the greatest challenges to the integrity of the developing dentition. Although the debates exist regarding the success rate of vital pulp therapy in cariously-exposed pulps, the technique is recommended to be performed on immature teeth [1,2].

Carious exposures in young permanent molars may cause irreversible damage to the pulp tissue and arrest root development, which can jeopardize the long-term tooth retention [3]. Hence, the main objective of treating carious-exposed immature teeth is to

maintain pulp vitality and enhance continuation of root development and apical closure. This approach is called apexogenesis. [4]

Vital pulp therapies should provide a biologically conductive environment for the pulp tissue to regenerate and prevent future bacterial contamination by using an appropriate pulp-capping agent. [3] The pulp capping material should possess biocompatibility, bactericidal effect, ensure a biologic seal, and induce hard tissue formation. [3,5]

A new era of regenerative endodontics recommended Mineral trioxide aggregate (MTA), to be considered the new gold standard for vital pulp therapies, that provides long-term seal, acceptable biocompatibility [6], and dentinal bridge formation as reported by various animal and human studies. [7,8] When the role of Calcium hydroxide (CH), that has been the most commonly used material for vital pulp therapy for many decades, was diminished, [9] claims raised against its use. The claims were attributed to several disadvantages including the exitance of tunnel defects in induced dentinal bridges, poor adherence to dentine, and lack of long-term seal. [10]

MTA is a powder that consists of fine hydrophilic particles that set in the presence of moisture. The setting time of MTA in moisture is less than 4h. MTA consists of tricalcium silicate, tricalcium aluminate, tricalcium oxide and silicate oxide. [11] MTA was considered a remarkable biocompatible material with various clinical applications that include surgical and non-surgical applications such as pulp capping [12], furcation and Perforation repairs [13], apexification and root end fillings [11,14]. Although the high clinical success of MTA material, there were always Issues prevented the clinicians to use it for many cases. The main reasons were related to very long setting time and difficult manipulation. [15]

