None needed.

12- Outcomes:

	Outcome	Tool/Device	Unit
Primary Outcome	spontaneous pain, sensitivity to percussion/ palpation)	Pain questionnaire	Binary
	Swelling or sinus tract	Visual examination by the third author	Binary
	Mobility	Back of the mirror	Binary
Secondary outcome	Stage of root development	Standardized periapical	3 stages
	Crown: Root ratio	Standardized periapical	2:1 ≥2:1
	Apex	Standardized periapical	Blunder apex, partially open, constricted
	Presence of radiolucency	Standardized periapical	Binary

Primary outcome:

Clinical assessment of the findings in the table will be conducted at follow up intervals (baseline, 6, 12 and 18 months)

Secondary outcome:

Radiographic assessment of stage of root development, crown: root ratio, apical closure and presence of radiolucency will be conducted through digital periapical radiographs by parallel

technique using film holders. The assessments will be carried out at follow up intervals (baseline, 6, 12 and 18 months)

13- Participants timeline:

	Study period				
	Enrolment	Allocation	Post allocation		Close out
Time point	For 7 months	0	6 months	12 months	18 months
Enrolment:					
Eligibility screen	✓				
Informed consent	✓				
History taking	✓				
Clinical examination	✓				
Preoperative radiograph	✓				
Allocation		✓			
Interventions:					
Access preparation		✓			
Placement of Biodentine (experimental group)		✓			
Placement of MTA (Control group)		✓			
Final restoration		✓			
Assessment					
Periapical radiograph as baseline reference			✓	✓	✓

Clinical examination to assess pain, swelling, fistula, tooth mobility			✓	✓	✓
Periapical radiograph to assess stage of root development, crown: root ratio, apical closure and presence of radiolucency			✓	✓	✓

14- Sample size calculation:

Sample size is calculated based upon the results of Alqaderi et al (2014) [15] who reported clinical success rate (primary outcome) for MTA = 90%. Since no relevant literature reported the clinical success rate of Biodentine in permanent teeth of pediatric patients, the success rate was assumed to be 50%. Using alpha level = 0.05 and β level = 0.20 (80% Power); the minimum estimated sample size will be 20 subjects per group for a total of 40 subjects. To compensate for a drop-out rate of 15%, the number is increased to 23 subjects per group for a total of 46 subjects.

Sample size calculation was performed using IBM® SPSS® Sample Power® Release 3.0.1.

15- Recruitment:

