All data will be collected, checked, revised, tabulated and entered into the computer. Qualitative data will be presented as frequencies and percentages. Since the study is a split-

mouth design; Wilcoxon signed-rank test will be used to compare between the two groups. Friedman's test will be used to study the changes by time within each group. Kaplan-Meier survival curve will be constructed to calculate the mean survival estimates of the two groups. Comparison between survival times will be performed using Log rank test.

The significance level will be set at $P \leq 0.05$. Statistical analysis will be performed with IBM® SPSS® Statistics Version 20 for Windows.

21-Monitoring:

The study data and results will be monitored regularly by the assessor who will have full access to these data.

22- Harms:

No reported adverse effects for both testing pulpotomy agents. Any adverse events appear during the trial will be recorded, documented and treated.

23-Auditing:

Auditing of the study design will be done by the evidence-based committee, Faculty of Dentistry -Cairo University.

V- Ethics and dissemination:

24-Research ethics approval:

This protocol and the template informed consent form will be reviewed by the Ethics Committee of Scientific Research - Faculty of Oral and Dental Medicine - Cairo University.

25-Protocol amendments:

Any modification to the protocol which may have an impact on the conduction of the study, potential benefit of the patient or my affect patient safety including, the changes of study objectives, study design, sample size or significant administrative aspects will require a formal amendment to the protocol.

26-Consent and Assent:

Researcher will discuss the trial with legal guardian of each participating child. They will be able to have an informed discussion with the researcher after explaining the procedure in simple words. Verbal assent will be taken orally from the participating child while written consent will be taken from the legal guardian of each participating child who is willing to participate in the

® IBM Corporation, NY, USA.

® SPSS, Inc., an IBM Company.

trial. All consent forms will be translated into Arabic.

27-confidentiality:

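### Section 20 names no comparison of the two materials on root development that accounts for the molar's recorded starting stage (secondary outcomes; a free improvement)

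*Combined protocol and SAP*

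**What the plan says.** All places are in the combined protocol and SAP.

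- **Aim.** The background in Section 6 says that treating these teeth should "maintain pulp vitality and enhance continuation of root development and apical closure". Section 7 sets the trial to compare the two materials for that purpose.
- **Outcomes.** Section 12 lists root stage (three classes), apex (three classes) and "Crown: Root ratio" (two classes) as secondary outcomes. Sections 12 and 18 schedule them at baseline and at months 6, 12 and 18. The diagnostic steps include a preoperative digital film.
- **Between-material test.** Section 20 states that the "Wilcoxon signed-rank test will be used to compare between the two groups". It names no outcome, visit, baseline term, or choice between raw and change values.
- **Change over time.** Section 20 adds: "Friedman's test will be used to study the changes by time within each group".
- **Design.** Section 8 describes parallel groups with equal allocation. Section 20 calls the trial split-mouth. Section 10 asks for affected molars on both sides.
- **Sample size.** Section 14 rests on clinical success alone: "the minimum estimated sample size will be 20 subjects per group for a total of 40 subjects", raised to 23 per group for drop-out. It gives no power for any root outcome.

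**The concern.** Continued root development means progress from where the molar started. A molar's stage at 18 months will usually depend on its stage at entry, so the entry stage carries information that a comparison of materials could use.

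As written, baseline has a definite place only in Friedman's test, which is run separately in each group. Two within-group tests do not compare the materials: one can be significant and the other not when the materials do not differ. The one named between-material test has no baseline term and leaves the visit and the value analysed open.

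Two things are at stake. Some power may be lost on the outcomes that describe apexogenesis, and the visit and value could be chosen after the data are seen.

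**Working it through.** **1. The plan's own figure.** Inputs from Section 14: success 90% and 50%, alpha 0.05 (taken as two-sided), power 80%. With pooled variance and mean proportion 0.70:

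n = [1.96 × √(2 × 0.70 × 0.30) + 0.842 × √(0.90 × 0.10 + 0.50 × 0.50)]² / 0.40² = (1.270 + 0.491)² / 0.16 ≈ 19.4, so 20 per group (power 81.3%).

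The step to 23 is 20 × 1.15. The figure reproduces and concerns clinical success only, so nothing below changes it.

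**2. What baseline can contribute in principle.** For a continuous outcome with baseline-to-18-month correlation ρ, the variance of the group difference relative to an unadjusted comparison is 1 − ρ² with baseline as covariate and 2(1 − ρ) for a change score.

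| ρ | covariate | change score |
|---|---|---|
| 0.3 | 0.91 | 1.40 |
| 0.5 | 0.75 | 1.00 |
| 0.7 | 0.51 | 0.60 |
| 0.8 | 0.36 | 0.40 |

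Since 1 − ρ² = (1 − ρ)(1 + ρ), the covariate factor never exceeds 2(1 − ρ). The change score is worse than no adjustment when ρ is below 0.5.

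**3. Three-class data, parallel reading.** Every input here is an assumption: latent normal root development cut into three equal stages, 20 per arm, true shift 0.9 SD, rank-based tests, 2,000 runs.

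| ρ | raw stage | baseline as covariate | change in stage |
|---|---|---|---|
| 0.3 | 69% | 71% | 50% |
| 0.5 | 70% | 76% | 59% |
| 0.7 | 68% | 85% | 75% |
| 0.8 | 70% | 91% | 85% |

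The covariate gains here are 2, 6, 17 and 21 points. A separate run gave 7, 16 and 23 points at ρ = 0.5, 0.7 and 0.8, hence about 2 to 23. Type I error of the covariate method was 4.7% to 6.1%.

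**4. Restricted baseline.** Section 10 admits only immature molars in children aged 7 to 8, so the entry stages may be concentrated. With baseline in two stages split 80/20, the gain was about 0 to 9 points. A separate run gave about 5, 9 and 12 points at ρ = 0.5, 0.7 and 0.8, so 12 is the highest seen with that split. With 90/10 it was about 3, 6 and 6 points.

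**5. Split-mouth reading.** With 20 pairs, the gain was about 1 to 18 points for evenly spread stages and 0 to 4 points for concentrated ones. In a separate 80/20 run (shift 0.6 SD) it was 2 to 8 points at left-right correlation 0.5, 2 to 3 at 0.7, and about zero at 0.9. The more alike a child's two molars are, the more the pairing has already done.

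**6. Chance imbalance, parallel reading only.** With 23 independent molars per group and half in the earliest stage (assumed), the SD of the gap between groups is √(2 × 0.25/23) = 0.147. P(gap of at least 20 points) = P(|Z| ≥ 0.20/0.147 = 1.36) = 0.175, or about 17%. This does not carry over to paired molars.

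**The case against.** Several stronger statements are tempting, and the documents do not support them.

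- **That raw stages are compared at each visit.** A reader might infer this, but Section 20 does not say so. What can be shown is that the value and visit are unspecified.
- **That baseline is ignored.** It is scheduled as an assessment, and Friedman's test can use it. It has no stated role in comparing the materials.
- **That the comparison is biased or invalid.** Randomisation protects an unadjusted test. This is a matter of efficiency and pre-specification.
- **That the power loss is large.** Gains near 20 points need evenly spread entry stages and a high correlation. The eligibility criteria make concentrated stages plausible, and pairing in a split-mouth trial already removes much of the variation between children.
- **That the two-class crown-to-root ratio must be replaced.** A median split of a normal measure keeps 2/π = 64% of the information, but the documents give neither the distribution nor the share in each class. The background in Section 6 notes magnification and distortion on periapical films, a plausible reason for coarse classes, and a molar has more than one root to choose from. Measuring the ratio is a trade-off.

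These objections limit the size of the point. They leave the gap in Section 20 in place. It can also be said that only a rank-based adjustment was simulated, so the behaviour of an ordinal or clustered model with 20 to 23 children has not been shown. That stands, and it bears on the choice of model.

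**Conclusion.** The point holds as a free improvement to the analysis of secondary outcomes. No stated test compares the materials on root development while accounting for the molar's recorded starting stage, and the visit and value for the between-material test are left open.

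The benefit cannot be sized from the documents. Under the stated assumptions it ranges from nothing to about 23 points of power in a parallel trial and to about 18 points in a split-mouth trial. If most molars enter at one stage, the benefit sits at the low end of those ranges. Adjustment cost no material power in these settings, and type I error stayed near 5%. The primary outcome and the planned sample size are untouched.

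**What to change.** 1. Reconcile Section 8 (parallel) with Section 20 (split-mouth) first, because this decides the form of the test.
2. In Section 20, name 18 months as the visit for the between-material comparison of root stage and apex. Include the molar's baseline category as a covariate, in a rank-based or ordinal model. If the trial is split-mouth, keep the pairing or cluster by child. The rank-based form is the one the simulations support; an ordinal or clustered model should be checked at this sample size before it is adopted.
3. Do not use a simple change in stage as the main comparison, since it can lose power. Keep Friedman's test as a within-group description.
4. Optional: record crown and root lengths on the existing films and analyse the measured ratio adjusted for its baseline. Do this only if the root to be measured is fixed in advance and measurement error is judged acceptable.

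The cost of items 1 to 3 is a few sentences in Sections 8 and 20 and a little more analysis. They need no new films, visits or patients. Item 4 adds measurement work.

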All patients attending the outpatient clinic in pediatric dentistry department complaining from carious mandibular first permanent molars will be screened and enrolled in the study if they meet the eligibility criteria.

16- Allocation:

Sequence generation:

Access cavity prepared molars will be assigned into experimental or control group using simple randomization 1:1 by the help of the computer software(random.org).

Allocation concealment mechanism:

Numbered opaque sealed envelopes.

Implementation:

The child will choose an envelope randomly and open it after caries removal so that the operator knows which pulpotomy agent will be used only after finishing the access cavity. Sequence generation will be done by the third author and the patient assignment will be done by the operator.

17- Blinding:

Patients and their parents, the assessor and the statistician will be blinded.

18- Data collection methods:**Primary outcome:**

Clinical assessment of the following findings:

1. postoperative pain: through asking the child and the parent if there is pain either continuous or intermittent
2. Swelling: through visual examination by the assessor either intraorally or extra-orally.
3. Sinus or fistula through visual examination of the gingiva by the assessor.
4. Tooth mobility: By the back of the mirror checked by the assessor to detect mobility in any direction

This assessment will be conducted every follow-up visit throughout the study period at baseline, 6, 12 and 18 months.

Secondary outcome

Radiographic assessment to detect stage of root development, crown: root ratio, apical closure and presence of radiolucency through standardized periapical radiograph by parallel technique using film holder. This assessment will be conducted every follow-up visit throughout the study period at baseline, 6, 12 and 18 months.

Postoperative records will be performed by the assessor to avoid individual variability and to promote data quality.

19- Data management:

Explanation to the parents about the importance of the follow-up visits in addition to treatment of other dental problems are plans to promotes participants retention and complete the follow-up. Also, phone calls before the dates before the next follow-up visit will be scheduled.

All findings will be documented in the examination sheet then transferred electronically to computer in secured lace sequentially.

20- statistical methods:

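### Section 20 pairs the two materials in the signed-rank test but not in the log-rank test, and the protocol does not settle on a design that would show which test is right

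*Combined protocol and SAP*

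**What the plan says.** Section 20 calls the study split-mouth and chooses its between-group test on that ground: "mouth design; Wilcoxon signed-rank test will be used to compare between the two groups". A few lines later, for the same two groups, it plans Kaplan-Meier curves and adds: "Comparison between survival times will be performed using Log rank test". Neither Section 20 nor any other section mentions stratification by child, a frailty term or a robust variance, so I read this as the ordinary log-rank test.

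The rest of the protocol describes the design in several ways:

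- Section 8: two parallel groups, equal allocation.
- Section 10: both mandibular first molars must be affected, so each child has two candidate molars.
- Section 14: "the minimum estimated sample size will be 20 subjects per group for a total of 40 subjects"; after allowance for drop-out, "the number is increased to 23 subjects per group for a total of 46 subjects".
- Section 16, sequence generation: "Access cavity prepared molars will be assigned into experimental or control group using simple randomization 1:1".
- Section 16, implementation: "The child will choose an envelope randomly and open it after caries removal so that the operator knows which pulpotomy agent will be used"; and "the patient assignment will be done by the operator".

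No passage says that a child's two molars receive different materials. Section 12 lists binary clinical signs as primary and radiographic findings as secondary: "Clinical assessment of the findings in the table will be conducted at follow up intervals (baseline, 6, 12 and 18 months". It names no time-to-event outcome.

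**The concern.** A signed-rank test needs one molar of each material in every child. The ordinary log-rank variance is right when molars are independent. Two molars in one mouth share diet, hygiene and host response, so positive correlation is plausible, and then the two tests rest on different designs.

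The direction of the log-rank error depends on how materials are distributed within a child. If every child has both, the variance is too large and precision is thrown away. If both molars of a child share one material, it is too small. With one molar per child the log-rank is right and the signed-rank test is the wrong one. As the protocol stands, a reader of the survival P-value could not tell which case applies.

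**Working it through.** **1. The plan's own figure.** Inputs from Section 14: success 90% (MTA) and 50% (Biodentine), alpha 0.05, power 80%. The two-independent-proportions formula, two-sided, with pooled variance (mean proportion 0.7):

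n = [1.96·√(2·0.7·0.3) + 0.8416·√(0.9·0.1 + 0.5·0.5)]² / (0.9 − 0.5)² = (1.270 + 0.491)² / 0.16 = 19.4, so 20 per group.

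This matches the plan, and 20 × 1.15 = 23. Section 14 therefore uses an independent-groups calculation, whereas Section 20 describes pairs.

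**2. Designs the text allows, against the two tests** (positive within-child correlation).

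| Design | Textual support | Signed-rank | Ordinary log-rank |
|---|---|---|---|
| Each child receives both materials | Sections 20, 10 | fits | valid, conservative |
| Both molars of a child receive one material | possible reading of Sections 8 and 16 | no cross-material pairs | anti-conservative |
| Molars randomized singly | Section 16, sequence generation | pairs in about half the children | about nominal on average |
| One molar per child | Section 14 | no pairs | correct |

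No row fits both tests.

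**3. Why the sign changes.** Let r be the correlation between the log-rank contributions of a child's two molars. The ordinary variance per child is proportional to 2. The true value is 2(1 − r) when the materials differ and 2(1 + r) when they are the same.

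In simulation with 23 split-mouth children and latent correlation 0.3 / 0.5 / 0.7, the ordinary variance was 1.23 / 1.50 / 2.02 times the true one. So r = 1 − 1/1.23 = 0.19, 1 − 1/1.50 = 0.33 and 1 − 1/2.02 = 0.50. The normal approximation then gives:

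- Different materials, 2[1 − Φ(1.96/√(1 − r))]: 3.0 / 1.6 / 0.5%.
- Same material, 2[1 − Φ(1.96/√(1 + r))]: 7.2 / 9.0 / 11.0%.

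**4. Simulation.** Gaussian-copula correlation between a child's molars, equal hazards at 6, 12 and 18 months, no drop-out, two-sided 5%, at least 20,000 trials per cell (Monte Carlo standard error about 0.15 points at 5%). The documents give no correlation and no null failure rate; 0.3 / 0.5 / 0.7 and 30% in both arms are assumptions.

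| Type I error, ordinary log-rank | 0.3 | 0.5 | 0.7 |
|---|---|---|---|
| Split-mouth, 23 children | about 3% | 1.7% | 0.7% |
| Same material in both molars | about 7% | 9% | 11% |
| Simple randomization of molars | about 5% | 5% | 5% |
| One molar per child | about 5% | 5% | 5% |

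| Power, 23 split-mouth children | 0.3 | 0.5 | 0.7 |
|---|---|---|---|
| 10% vs 50% failure: ordinary | 91% | 92% | 93% |
| 10% vs 50%: child-level test | 91% | 95% | 98% |
| 10% vs 50%: stratified by child | 88% | 93% | 98% |
| 10% vs 30%: ordinary | 40% | 39% | 38% |
| 10% vs 30%: child-level test | 41% | 46% | 54% |

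The 10% vs 50% rows are Section 14's success rates turned into failures; 10% vs 30% is a smaller effect of my choosing. With 46 split-mouth children, power at 10% vs 50% is above 99% for both the ordinary and the child-level test. Type I error under split-mouth at 30% failure is about 4 to 5% for the child-level test and 4.3 to 4.6% for the stratified one (23 children).

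**The case against.** The strongest reply is that Section 20 does say split-mouth. On that reading the log-rank errs on the safe side, costs at most about 5 points of power at the planned effect with 23 children and almost nothing with 46, and concerns an analysis that Section 12 does not list. The underlying fault is then the unsettled design, and the choice of test follows once that is settled. Most of this stands, and it limits the weight of the point. It does not remove it: under split-mouth the log-rank sentence would still ignore the pairing that the same paragraph invokes.

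A reader might infer from Section 16 that the log-rank produces too many false positives, because the child draws one envelope and the operator makes a patient assignment. The documents do not support that as a finding. No passage says that both molars receive one material. Section 16 randomizes molars, and the envelope is opened once a cavity is prepared, so it may cover that molar alone, or fix the first molar and leave the alternative for the second. The 7 to 11% figures describe a possible but less supported reading.

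A reader might also infer that the primary comparison is invalid. This point does not show that.

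Finally, the correlations are assumed. At zero correlation the ordinary log-rank holds its level in every design examined here at 30% failure.

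**Conclusion.** The inconsistency is real and should be corrected before analysis, as a secondary matter. The two tests in Section 20 assume different things about the molars, and five sections leave the design open.

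If split-mouth governs, the consequence is a conservative survival test: lost precision that matters little at the planned difference and more at smaller ones. Inflation arises only if both molars of a child share a material. Under simple randomization of molars, or with one molar per child, the test to replace is the signed-rank.

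The direction of each error needs only positive within-child correlation. The sizes rest on the assumed correlations, the assumed 30% null failure rate, the visit schedule and no drop-out.

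**What to change.** 1. Reconcile Sections 8, 14, 16 and 20 on one design. State how many molars each child contributes, whether a child's two molars receive different materials, and whether the 46 in Section 14 are children or molars. Restate the sample-size basis to match. Define the failure event for the survival analysis, since Section 12 lists only separate signs.

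2. If every child receives both materials, keep the signed-rank test and replace the log-rank sentence with one of two tests:
   - A child-level log-rank score test, with the formula written into Section 20. At each visit let D of N molars at risk fail, N1 of the N being Biodentine. For a molar, let Y mark at risk, d failure and X Biodentine. Then S_i = sum over child i's molars and visits of (d − Y·D/N)(X − N1/N), and the statistic is (ΣS_i)² / ΣS_i² on 1 df. A verbal description is not enough: other contributions with the same total gave type I errors of 6.4 to 7.3% or 0.2 to 0.8%, and a centred variance with factor n/(n − 1) gave 5.6 to 6.0%.
   - A log-rank stratified by child. It holds its level but loses power if correlation is near zero (82% against 88% for the ordinary test at 10% vs 50%).

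3. If children contribute two molars but not always one of each material, use the child-level test rather than stratification, which under simple randomization of molars gave 50 to 72% power against 87 to 88%. Replace the signed-rank test with an unpaired comparison that accounts for clustering by child.

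4. If each child contributes one molar, keep the ordinary log-rank and replace the signed-rank test with an unpaired test.

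The cost is the design wording, a sample-size restatement, minor analysis work, and a check that the software named in Section 20 can compute the chosen test. With 23 split-mouth children and zero correlation, the child-level test lowers power at 10% vs 50% from 88% to 86%. If failure is only 10% in both arms, its type I error is no nearer nominal overall (2.6 / 2.2 / 1.4% against 3.0 / 2.0 / 1.0%). With same-material molars in 23 children, power at 10% vs 50% falls from about 85 / 83 / 82% to 77 / 72 / 68%, partly the price of removing the inflated type I error.

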Clinical and Radiographic Evaluation of MTA versus Biodentine as Pulpotomy Agents in Immature First Permanent Molars: A Randomized Clinical Trial

Protocol submitted to the Faculty of Dentistry, Cairo University
by
[name]
Associate Professor of Pediatric Dentistry

Faculty of Dentistry
Cairo University
18 Jan 2017

I. Administrative information:

1. Title:

Clinical and Radiographic Evaluation of MTA versus Biodentine as Pulpotomy Agents in Immature First Permanent Molars: A Randomized Clinical Trial

2. Protocol Registration:

To be registered on Clinicaltrial.gov

3. Protocol version:

Final version.

4. Funding:

This trial is self-funded.

5. Roles and responsibilities:

1. **[name] ([name])** Associate Professor of Pediatric Dentistry, Cairo University. Responsible for the clinical part of study, and Data monitoring.
2. **[name] ([name])** Professor of Pediatric Dentistry, National University of Singapore, responsible for the writing revision and proof reading.
3. **[name] ([name])** Associate Professor of Pediatric Dentistry, Misr University for sciences and technology. Responsible for the clinical evaluation of the cases at the evaluation intervals

II. Introduction

6-background and rationale:

Description of research question:

P: children with cariously exposed immature mandibular first permanent molars

I: Pulpotomy using Biodentine

C: MTA pulpotomy

O:

	Outcome	Tool/Device	Unit
Primary Outcome	spontaneous pain, sensitivity to percussion/palpation)	Pain questionnaire	Binary
	Swelling or sinus tract	Visual examination by the third author	Binary
	Mobility	Back of the mirror	Binary
Secondary outcome	Stage of root development	Standardized periapical	3 stages
	Crown: Root ratio	Standardized periapical	2:1 ≥2:1
	Apex	Standardized periapical	Blunder apex, partially open, constricted
	Presence of radiolucency	Standardized periapical	Binary

S: Randomized clinical trial

T: 18 months (Baseline, 6, 12 and 18 months)

Research question: is Biodentine used as pulpotomy material in cariously exposed immature mandibular first permanent molars more successful clinically and radiographically than MTA pulpotomy?

Justification for undertaking the trial:

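### The radiographic half of the research question rests on four unranked secondary outcomes over three visits at an unadjusted P ≤ 0.05, with no key contrast, main visit or exploratory label

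*Combined protocol and SAP*

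**What the plan says.** The research question in Section 6 asks whether Biodentine is "more successful clinically and radiographically than MTA pulpotomy". Section 7 likewise sets out to compare both kinds of outcome. The rationale in Section 6 gives continued root development and closure of the apex, together with pulp vitality, as the aim of treatment.

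Section 12 puts the clinical findings in the primary tier and four radiographic findings in the secondary tier: "Radiographic assessment of stage of root development, crown: root ratio, apical closure and presence of radiolucency will be conducted". None of the four is ranked, and no composite of radiographic success is defined. Section 18 says of the radiographic readings: "This assessment will be conducted every follow-up visit throughout the study period at baseline, 6, 12 and 18 months".

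Section 20 compares the materials with the Wilcoxon signed-rank test, without saying for which outcomes or visits. It adds that "Friedman's test will be used to study the changes by time within each group", plans Kaplan-Meier curves with a log-rank test, and closes with "The significance level will be set at $P \leq 0.05". It gives no order of testing, adjustment, main visit or statement that any result is exploratory.

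**The concern.** The research question invites a conclusion that one material is radiographically better, but the plan does not say which result would support it. Apex might differ at 6 months and not at 18, or crown:root ratio might differ while radiolucency does not. Nothing settles beforehand which of these answers the question, so the choice could be made after the data are seen.

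Three of the four outcomes (root stage, crown:root ratio and apex) are overlapping readings of the same root on the same film. One underlying question therefore gets several chances to reach P ≤ 0.05. At stake is a published claim of radiographic superiority for either material that rests on a chance finding.

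**Working it through.** **The plan's own figure.** The only error rate and power in the plan belong to the clinical primary outcome. Section 14 takes the MTA rate from a study "who reported clinical success rate (primary outcome) for MTA = 90" per cent, and for Biodentine "the success rate was assumed to be 50" per cent, with alpha 0.05 and 80% power. The pooled two-sided formula gives

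n = [1.96·√(2·0.7·0.3) + 0.8416·√(0.9·0.1 + 0.5·0.5)]² / 0.4² = (1.270 + 0.491)² / 0.16 = 19.4, so 20 per group.

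This matches the plan, and 20 × 1.15 = 23 matches the dropout allowance. The plan states no error rate for the radiographic set.

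**Number of tests.** A signed-rank test uses one difference per pair, so it does not pool three visits. The natural reading is 4 outcomes × 3 post-treatment visits = 12 tests. The narrower reading, 18 months only, gives 4. Not counted are baseline comparisons, the 4 × 2 = 8 within-group Friedman tests, which do not compare the materials, and the log-rank test, which is not tied to any radiographic outcome.

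**Independent tests.** P(at least one P ≤ 0.05) = 1 − 0.95^k.
- k = 12: 1 − 0.540 = 0.460
- k = 4: 1 − 0.8145 = 0.1855

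**Correlated tests, normal model.** P(any |Z| > 1.96) with a common correlation, 200,000 draws:

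| Correlation | 0 | 0.3 | 0.5 | 0.7 | 0.8 | 0.9 |
|---|---|---|---|---|---|---|
| 12 tests | 0.46 | 0.395 | 0.318 | 0.233 | 0.186 | 0.135 |
| 4 tests | 0.185 | 0.174 | 0.155 | 0.130 | 0.115 | 0.093 |

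**Signed-rank simulation on categories.** These runs used three-class and binary outcomes, 20 to 23 pairs and no true difference. Category frequencies and correlations are assumptions.

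| Assumed pattern | 12 tests | 18 months only |
|---|---|---|
| Categories well spread or changing slowly, moderate correlation | 0.31–0.38 | 0.13–0.17 |
| Same, visit and outcome correlation 0.9 | 0.22–0.28 | 0.08–0.14 |
| Nearly all teeth in one category at each visit | 0.06–0.26 | 0.02–0.10 |

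The 0.22 is a single setting with slow change and every correlation at 0.9; the others in that row are about 0.25 or more. Ties explain the last row: with few discordant pairs each test rejects less than 5% of the time. At high correlation the normal model falls below the categorical simulation, because coarse categories correlate less strongly than the underlying values.

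**Pair count.** Section 8 describes parallel groups. Section 20 describes a split-mouth design, and Section 10 asks for bilaterally affected molars. If the number of pairs were 40 to 46 rather than 20 to 23, the simulated rate over 12 tests would be about 0.34–0.43.

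**Effect of the remedy.** One pre-named radiographic test has an error rate of 0.05. Dividing alpha would need 0.05/4 = 0.0125 for the four 18-month tests or 0.05/12 = 0.0042 for all 12.

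**The case against.** The strongest reply is that these are secondary outcomes in a small, self-funded academic trial that is sized on clinical success alone, and that many such trials do not control error formally across secondary outcomes. A reader might infer that the plan has no hierarchy at all, or that its main analysis is inflated. The documents do not support that: a primary and a secondary tier exist, and the radiographic outcomes sit in the lower one. What is missing is a rule inside that tier. The tier label does not say whether a radiographic P ≤ 0.05 may support a claim, and the research question asks for one.

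The second reply is that Section 20 never says a test is run at each visit; Sections 12 and 18 schedule assessments, not tests. This stands. A reader might infer that the plan prescribes 12 tests and lets any one of them decide, but neither is written. If only 18 months is tested, the figure is much smaller. Even then the plan would need to say so and to rank four outcomes.

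The third reply concerns the size. A reader might take roughly a third as the trial's false-positive rate. It is a plausible middle value under 12 tests and moderate correlation, but the documents give no correlation or category frequency that would establish it. The overlap among the root readings argues for strong correlation, and excluding teeth with lesions at entry argues for few radiolucencies and many ties. Both pull the figure down.

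**Conclusion.** The concern holds as a gap within the secondary tier. The radiographic half of the research question has several unadjusted chances of a false positive and no rule for which result counts.

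On the 12-test reading the chance of at least one spurious P ≤ 0.05 is 46% if the tests are independent, about 24–38% under moderate to strong correlation with spread categories, and about 6–26% if most teeth share a category. On the 18-month reading it is at most about 18.5%, typically 9–16%, and near or below 5% when heavy ties combine with strong correlation. All of these except the independent figures rest on assumed correlations, and the categorical ones also on assumed frequencies and pair numbers. The missing rule does not depend on them. This is a worthwhile, inexpensive improvement, not a fault in the primary analysis.

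**What to change.** Add to Section 20 wording such as:

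> The radiographic comparison between materials is apical closure at 18 months, tested at two-sided 0.05 as a secondary result. The other radiographic outcomes, all 6- and 12-month radiographic comparisons and the within-group Friedman tests are exploratory. They are reported as frequencies, with between-group differences and 95% confidence intervals where the materials are compared, and no claim that one material is better rests on them.

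Apical closure is an example, chosen because it is part of the treatment aim in Section 6. Root stage has a similar claim. The sponsor may name another single outcome at 18 months, provided this is done before unblinding.

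The test should not be made conditional on a significant clinical result. Sections 12 and 18 list several clinical findings at several visits, and the plan defines no single clinical comparison on which such a condition could rest. Sections 8 and 20 must also be reconciled on parallel versus split-mouth design, so that the named comparison has a test that fits.

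The cost is a few sentences, with no new patients, visits or data. The downside is that an isolated P ≤ 0.05 on another radiographic outcome, or at an early visit, can no longer be presented as a confirmed difference.
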